5.2 Procedures

(STROBE 5; swissethics 3a) [6,69]

Work package I: 'preschool'

Step 1: recruitment (see 2.4). During the recruitment besides the parent information leaflets and consents, the questionnaire will be distributed to parents. They will be asked to bring the filled-in Luftibus questionnaire on the day of SESI-MS measurement. Asthma risk will be assessed applying the modified asthma predictive index (mAPI) and the Leicester prediction tool to categorise patients to high or low asthma risk groups.

Step 2: measurement visit: All children will undergo a short clinical assessment by the attending physician. Weight and body-length will be measured as per clinical requirements. Information on actual treatment and last medication (if applicable), last food intake will be gathered. Participants will be thoroughly examined for atopic dermatitis during the medical visits, using the SCORing Atopic Dermatitis method (SCORAD), performed by a medical doctor.

All measurements will be performed at the Kinderspital Zurich.

Prior to the measurement, participants will need to have abstained for at least one hour from passive smoking, eating (including chewing gum), beverages (except for plain water), brushing of teeth and using mouthwash. This should cause minimal discomfort, as participants are free to indulge in normal daily activities and dietary habits up to one hour before the beginning of the test session and immediately after its completion.

SESI-MS measurement:

- Children 1.5-4 years of age: for the breath analysis children are comfortably seated on a chair or on the lap of the parent and will be asked to breathe calmly as they usually breathe for about 15 seconds through a sterile mask into the mass spectrometer.
- Infants <1.5 years of age: measurements will be performed while the child is in natural sleep. The child will be in supine position either on the lap of the mother or in the cot. The face mask will be carefully placed over the nose and mouth of the sleeping child. This procedure is entirely risk-free as no alteration of normal breathing is required. After six breath cycles of 15 seconds over a period of several minutes, measurement is complete.

Allergy testing:

Skin-prick test (SPT) for the 7 most common aeroallergens in Switzerland (*D. pteronissimus*, cat, grass mix, birch, hazelnut, ash, and alder) will be performed in all healthy controls and children with respiratory symptoms \geq 2y whom allergy testing has never been performed before. Results from allergy testing for most of the patients with respiratory symptoms is available routine clinical laboratory testing.

SPT is a simple, safe and quick test, providing results within 15-20 minutes. A drop of the allergen (extract) solution is placed on the skin of child comfortably seated on a chair or on the lap of the parent. The skin is then pricked through the drop using the tip of a lancet – this can feel a little sharp but is not painful and should not bleed. In case of sensitization to an allergen it elicits a small, localised allergic response, in the form of a wheal (bump) and flare (redness) at the site of testing, which disappears within 15 minutes. In the standard procedure local antihistamine gel is applied after the test to avoid itching.

Throat swab

Airway and oral bacteria are metabolically active and may add to the exhaled volatile metabolites. Therefore, airway cultures need to be assessed in all children. Throat swab: a small cotton will be used to swab the posterior nasopharynx and then placed into the culture medium.

Fractional exhaled Nitric oxide (FeNO):

The fraction of exhaled nitric oxide (FeNO) is a non-invasive biomarker associated with airway inflammation and can be measured across all ages in standardized fashion. For the reservoir-offline technique, children are sitting on the legs of the parent or a chair while tidally breathing NO-free air for ten breaths. A reusable inert collection bag is attached to the expiratory side of a non-rebreathing valve

with a resistor in place. Five breaths during relaxed tidal breathing will be sampled, and FeNO will be analysed within 4 hours using a chemiluminescence analyser. FeNO will be assessed in healthy controls only.

The whole procedure will take 40 minutes.

Work package II 'longitudinal':

Step 1: all the subjects from WP I will be asked to continue their participation in WP II. The scheme of the visits will be presented to parents

Step 2; Interim visits (yearly): all children will undergo a short clinical assessment by the attending physician. Weight and body-length will be measured as per clinical requirements. Information on actual treatment and last medication (if applicable), last food intake will be gathered. Participants will be thoroughly examined for atopic dermatitis during the medical visits, using the SCORing Atopic Dermatitis method (SCORAD), performed by a medical doctor.

All measurements will be performed at the Kinderspital Zurich.

Prior to the measurement, participants will need to have abstained for at least one hour from passive smoking, eating (including chewing gum), beverages (except for plain water), brushing of teeth and using mouthwash. This should cause minimal discomfort, as participants are free to indulge in normal daily activities and dietary habits up to one hour before the beginning of the test session and immediately after its completion.

SESI-MS measurement:

- Children 1.5-4 years of age: for the breath analysis children are comfortably seated on a chair or on the lap of the parent and will be asked to breathe calmly as they usually breathe for about 15 seconds through a sterile mask into the mass spectrometer.
- Infants <1.5 years of age: measurements will be performed while the child is in natural sleep. The child will be in supine position either on the lap of the mother or in the cot. The face mask will be carefully placed over the nose and mouth of the sleeping child. This procedure is entirely risk-free as no alteration of normal breathing is required. After 6 breath cycles of 15 seconds over a period of several minutes, measurement is complete.
- Children ≥4 years of age: measurements will be performed via a mouthpiece. Comfortably seated participants will be asked to exhale calmly for about 15 seconds through a sterile plastic mouth piece into the MS. This procedure is entirely risk-free as no alteration of normal breathing is required it is less demanding than routine spirometric testing. After six repeated exhalations over a period of several minutes, testing is complete.

Spirometry

Lung function will be measured in all children ≥4 years of age. In the case of a recent lung function measurement (less than 2 weeks prior to the study date) no spirometry will be performed. This is a standard procedure routinely used in medical praxis to assess the lung function. The children are asked to take the deepest breath they can, and then exhale into the lung function mouth piece as hard as possible, for as long as possible, preferably at least 6 seconds. During the test, soft nose clips may be used to prevent air escaping through the nose. Sterile single use filter mouthpieces are used to prevent the spread of microorganisms.

Fractional exhaled Nitric oxide (FeNO):

The fraction of exhaled nitric oxide (FeNO) is a non-invasive biomarker associated with airway inflammation and can be measured across all ages in standardized fashion. For the reservoir-offline technique, children are sitting on the legs of the parent or a chair while tidally breathing NO-free air for ten breaths. A reusable inert collection bag is attached to the expiratory side of a non-rebreathing valve with a resistor in place. Five breaths during relaxed tidal breathing will be sampled, and FeNO will be analysed within 4 hours using a chemiluminescence analyser.

Throat swab

Airway and oral bacteria are metabolically active and may add to the exhaled volatile metabolites. Therefore, airway cultures need to be assessed in all children. Throat swab: a small cotton will be used to swab the posterior nasopharynx and then placed into the culture medium

Exhaled breath condensate:

EBC are collected by a simple glass cold trap which is placed into a cooling sludge (T = -78.5° C, isopropanol/dry ice) following the guidelines by the ATS/ERS task force [77]. The cold trap is fixated on a table for safety and an exhaust line is applied to the cooling sludge to avoid any possible fumes from the isopropanol. The child breathes through a disposable, sterile mouthpiece into a teflon line connected to the cold trap during 5-15 minutes. The samples are immediately stored at -80°C until up-concentration by lyophilisation and analysis with ultra- high performance liquid chromatography high resolution tandem mass spectrometry (UHPLC-HRMS/MS) at either the Kinderspital Zurich or ETH Zurich.

Step 2; the last visit: all the procedures from interim visits will be repeated. In addition the second SPT will be performed to healthy controls and children with respiratory symptoms who don't have any allergy testing within last 3 months.

WP III 'school-age'

Step 1: recruitment (see 2.4). During the recruitment besides the parent information leaflets and consents, the questionnaires will be distributed to parents. They will be asked to bring the filled-in questionnaires on the day of SESI-MS measurement. Asthma risk will be assessed applying the modified asthma predictive index (mAPI) and the Leicester prediction tool to categorise patients to high or low asthma risk groups.

Step 2: measurement visit: All children will undergo a short clinical assessment by the attending physician. Weight and body-length will be measured as per clinical requirements. Information on actual treatment and last medication (if applicable), last food intake will be gathered. Participants will be thoroughly examined for atopic dermatitis during the medical visits, using the SCORing Atopic Dermatitis method (SCORAD), performed by a medical doctor.

All measurements will be performed at the Kinderspital Zurich.

Prior to the measurement, participants will need to have abstained for at least one hour from passive smoking, eating (including chewing gum), beverages (except for plain water), brushing of teeth and using mouthwash. This should cause minimal discomfort, as participants are free to indulge in normal daily activities and dietary habits up to one hour before the beginning of the test session and immediately after its completion.

SESI-MS measurement:

Measurements will be performed via a mouthpiece. Comfortably seated participants will be asked to exhale calmly for about 15 seconds through a sterile plastic mouth piece into the MS. This procedure is entirely risk-free as no alteration of normal breathing is required – it is less demanding than routine spirometric testing. After six repeated exhalations over a period of several minutes, testing is complete.

Spirometry

Lung function will be measured in all children \geq 4 years of age. In the case of a recent lung function measurement (less than 2 weeks prior to the study date) no spirometry will be performed. This is a standard procedure routinely used in medical praxis to assess the lung function. The children are asked to take the deepest breath they can, and then exhale into the lung function mouth piece as hard as possible, for as long as possible, preferably at least 6 seconds. During the test, soft nose clips may be used to prevent air escaping through the nose. Sterile single use filter mouthpieces are used to prevent the spread of microorganisms.

Fractional exhaled Nitric oxide (FeNO):

The fraction of exhaled nitric oxide (FeNO) is a non-invasive biomarker associated with airway inflammation and can be measured across all ages in standardized fashion. For the reservoir-offline technique, children are sitting on the legs of the parent or a chair while tidally breathing NO-free air for ten breaths. A reusable inert collection bag is attached to the expiratory side of a non-rebreathing valve with a resistor in place. Five breaths during relaxed tidal breathing will be sampled, and FeNO will be analysed within 4 hours using a chemiluminescence analyser.

Throat swab

Airway and oral bacteria are metabolically active and may add to the exhaled volatile metabolites. Therefore, airway cultures need to be assessed in all children. Throat swab: a small cotton will be used to swab the posterior nasopharynx and then placed into the culture medium. In expectorating CF patients a sputum sample will be collected.

Exhaled breath condensate:

EBC are collected by a simple glass cold trap which is placed into a cooling sludge (T = -78.5° C, isopropanol/dry ice) following the guidelines by the ATS/ERS task force [77]. The cold trap is fixated on a table for safety and an exhaust line is applied to the cooling sludge to avoid any possible fumes from the isopropanol. The child breathes through a disposable, sterile mouthpiece into a teflon line connected to the cold trap during 5-15 minutes. The samples are immediately stored at -80°C until up-concentration by lyophilisation and analysis with ultra- high performance liquid chromatography high resolution tandem mass spectrometry (UHPLC-HRMS/MS) at either the Kinderspital Zurich or ETH Zurich.

Allergy testing:

Skin-prick test (SPT) for the 7 most common aeroallergens in Switzerland (*D. pteronissimus*, cat, grass mix, birch, hazelnut, ash, and alder) will be performed in all healthy controls and children with respiratory symptoms \geq 2y whom allergy testing has never been performed before. Results from allergy testing for most of the patients with respiratory symptoms is available routine clinical laboratory testing. SPT is a simple, safe and quick test, providing results within 15-20 minutes. A drop of the allergen (extract) solution is placed on the skin of child comfortably seated on a chair or on the lap of the parent. The skin is then pricked through the drop using the tip of a lancet – this can feel a little sharp but is not painful and should not bleed. In case of sensitization to an allergen it elicits a small, localised allergic response, in the form of a wheal (bump) and flare (redness) at the site of testing, which disappears within 15 minutes. In the standard procedure local antihistamine gel is applied after the test to avoid itching.

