5.1 Type of research and general project design (STROBE 4)

Type: observational

Single center

Design:	
WP 1 / WP III	Cross sectional case control study
WPII	Longitudinal cohort study
WP IV	longitudinal assessment of asthma worsening

Our project will consist of four work packages (WP):

WP I 'preschool'; prospective cross-sectional exploratory observational matched case control study:

WP I will consist of age and sex matched case-control study including 180 preschool children aged 6 months to 4 years. It is designed for phenotyping children with chronic respiratory symptoms by SESI-MS.

Three groups will be investigated:

Healthy controls (n=60) and two groups cases stratified by diagnostic certainty: A) patients with chronic respiratory symptoms (wheezing, cough) and low risk for asthma (n=60) and B) patients with chronic respiratory symptoms (wheezing, cough) and high risk for asthma (n=60).

Asthma risk will be assessed applying the modified asthma predictive index (mAPI) and the Leicester prediction tool [14,66].

WP II 'longitudinal'; prospective longitudinal observational cohort study: For prospective assessment of health outcomes parents of the participants of WP I will be asked to take part in longitudinal follow-up study. Participants will be followed until reaching the age where lung function testing reliably can be conducted (six years). Therefore, the duration of the follow depends on the age at study entry (two to six years). Two follow-up schemes will be offered:

- 1. This scheme consists of one follow-up visit at the age six. We aim for a participation of rate 75% (n=135) of the WP I population.
- 2. For this scheme parents will be offered yearly follow-up visits until the age of six. We aim to recruit at least 45 healthy controls, 45 patients with chronic respiratory symptoms (wheezing, cough) and low risk for asthma, and 45 patients with chronic respiratory symptoms (wheezing, cough) and high risk for asthma

WP III 'school-age'; prospective cross-sectional exploratory observational matched case control study: In this case-control study we enrol three groups with sex- and age-matched school-aged children (age 5 - 18 years): A) healthy controls (n=30), B) children with known allergic asthma (n=30) and C) children with known non-allergic asthma (n=30).

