6. PROJECT POPULATION

(STROBE 6; HRO Annex 2/1.2) [4,6]

As our study approach is exploratory, thus the possibilities for sample size estimation are limited.

WP I 'preschool': 180 preschool children aged 6 months to 4 years will be included in WP 1.

Three groups will be investigated:

- 60 Healthy controls
- 60 Patients with chronic respiratory symptoms (wheezing, cough) and low risk for asthma
- 60Patients with chronic respiratory symptoms (wheezing, cough) and high risk for asthma

WP II 'longitudinal'; prospective longitudinal observational cohort study: For prospective assessment of health outcomes parents of the participants of WP I will be asked to take part in longitudinal follow-up study. Participants will be followed until reaching the age where lung function testing reliably can be conducted (six years). Therefore, the duration of the follow depends on the age at study entry (two to six years). Two follow-up schemes will be offered:

This scheme consists of one follow-up visit at the age six. We aim for a participation of rate 75% (n=135) of the WP I population.

- 45 healthy controls
- 45 patients with chronic respiratory symptoms (wheezing, cough) and low risk for asthma
- 45 patients with chronic respiratory symptoms (wheezing, cough) and high risk for asthma

WP III 'school-age'; prospective cross-sectional exploratory observational matched case control study:

In this case-control study we enrol three groups with sex- and age-matched school-aged children (age 5 - 18 years):

- 30 healthy controls
- 30 children with known allergic asthma
- 30 children with known non-allergic asthma

WP IV: 'school-age' assessment during asthma worsening.

Patients from WP III will be asked to return for two additional visits in the case of an asthma worsening. Visit Ex1 will be done within 1 week of start of asthma worsening and Visit Ex2 one month after asthma worsening is resolved. Patients with the need of an acute treatment with systemic corticosteroids or hospitalization will not be included in this part.

We aim to include 10-15 asthmatic patients from WP III

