6.1 Inclusion criteria

All WP:

- informed consent by parents (and by children if age > 8 years)
- active/passive understanding of German or other languages spoken in Switzerland
- No chronic respiratory symptoms or diseases in healthy controls

WP I and II:

All groups:

• age 6 months -4 years

Wheeze group:

• preschool wheeze (more than two episodes of wheeze during 12 months prior to inclusion) Cough group:

• daily cough for at least 4 weeks prior to inclusion

WP III:

All groups:

• age 5 years - < 18 years

Asthma group:

• doctor diagnosed asthma (according to current guidelines)

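### WP III accepts allergy results of any age for asthmatic patients and contradicts the protocol's other sections on who is skin-tested, so the allergic versus non-allergic contrast may be diluted

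*Protocol*

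**What the plan says.** Protocol section 5.1 defines the two asthma groups of WP III as "children with known allergic asthma (n=30) and C) children with known non-allergic asthma (n=30"; section 6 repeats this ("30 children with known non-allergic asthma"). Section 6.1 asks only for "doctor diagnosed asthma (according to current guidelines" and gives the age range as "age 5 years - < 18 years". No section names a test, panel, positivity criterion or date for the split.

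Four places say who is allergy-tested:

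- **Section 5.2, WP III, Allergy testing:** SPT with seven aeroallergens in all healthy controls, and in symptomatic children aged 2 years or more "whom allergy testing has never been performed before". For the others: "Results from allergy testing for most of the patients with respiratory symptoms is available routine clinical laboratory testing".
- **Schedule of Assessments:** SPT is marked at the WP III visit with no exemption.
- **Section 6.6, Allergy testing:** SPT is described for healthy controls only. Patients' results are said to be available for children with cystic fibrosis, a disease that section 6.2 excludes.
- **Section 5.2, WP II, last visit:** SPT is repeated in healthy controls and in "children with respiratory symptoms who don't have any allergy testing within last 3 months".

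**The concern.** Allergic status separates two of the three WP III groups and underlies the hypothesis in section 4.1 that asthma can be phenotyped by breathprint. Under the WP III text of section 5.2, a patient with any previous allergy test gets no study SPT, however old that test is and whatever it covered. A negative result from the preschool years can then stand beside a breath measurement taken in adolescence.

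If such a child has become sensitised since, the non-allergic group contains a child who belongs with the allergic asthmatics. That pulls the two groups together and favours a finding of no difference. The protocol's own background (section 3.1.4.2) reports that raised exhaled nitric oxide in persistent wheezers was confined to sensitised children, so it expects sensitisation to matter for exhaled markers. If current status was never measured, no later analysis can restore it.

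**Working it through.** **1. The texts side by side, for an asthmatic child in WP III**

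| Place | Child never tested | Child with an old test |
|---|---|---|
| Section 5.2, WP III | SPT | no SPT |
| Schedule of Assessments | SPT | SPT |
| Section 6.6 | not described | not described |

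The three places give three different answers. For comparison, the WP II last visit would retest the child with an old test unless that test fell within 3 months.

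**2. How old an accepted result can be.** A result cannot be older than the child. The WP III sentence is the same as the WP I sentence in section 5.2, including the limit of 2 years or more, which excludes nobody in WP III because every child is at least 5. In WP I (6 months to 4 years) an old result is at most 4 years old. In WP III (5 to under 18 years) the same bound is nearly 18 years.

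**3. Size of the dilution.** There is no planned figure to reproduce: section 7.1 gives no alpha, power, effect size or standard deviation for WP III. The only input from the documents is n = 30 per group. Assumptions: a share m of the non-allergic group is in truth sensitised, those children resemble the allergic group on average, the allergic group is pure, and the within-group variance is unchanged.

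- Mean of the labelled non-allergic group = (1-m) × non-allergic mean + m × allergic mean.
- Observed difference = (1-m) × true difference.
- Equivalent correctly classified n per group = 30 × (1-m)².

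| m | Children of 30 | Difference retained | Equivalent n |
|---|---|---|---|
| 10% | 3 | 90% | 30 × 0.81 = 24.3 |
| 20% | 6 | 80% | 30 × 0.64 = 19.2 |
| 30% | 9 | 70% | 30 × 0.49 = 14.7 |

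**4. The same in power terms.** Assume a two-sided alpha of 0.05, SD 1 and the normal approximation. With 30 per group the standardised difference detectable with 80% power is (1.960 + 0.842) × √(2/30) = 0.72.

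| m | Power, true difference 0.72 | n per group for 80% | Power, true difference 1.0 |
|---|---|---|---|
| 0 | 80% | 30 | 97% |
| 10% | 71% | 37 | 94% |
| 20% | 61% | 47 | 87% |
| 30% | 50% | 62 | 77% |

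Section 7.3 plans Bonferroni-corrected Kruskal-Wallis tests per peak, so absolute power would be lower than shown. The table conveys direction and relative loss only.

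**The case against.** A reader might infer that the protocol splits allergic from non-allergic asthma by any test ever done, that previously tested children are never retested, and that sensitised children are in fact counted as non-allergic. The documents do not support any of these.

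- Section 5.2 says who receives a study SPT. It does not say that this forms the groups, which are described only as 'known' types.
- The Schedule marks an SPT at the visit. Patients come from regular asthma follow-up (section 5.1), where the clinic may have retested them, and section 6.6 allows specific IgE if clinically indicated.
- No test dates and no rate of new sensitisation are given, so misclassification is possible but not shown.

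All of this stands, and it limits the point to what may happen if section 5.2 is followed as written.

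The WP II comparison is also weaker than it looks. Its 3-month rule governs a repeat SPT at the end of a longitudinal follow-up, and the Schedule marks SPT at every WP II visit from 2 to 6 years, so WP II is not settled either. Copying that rule would still mix routine tests with the study panel. Letting a negative seven-allergen SPT override a documented sensitisation to another allergen would create new misclassification. These objections shape the remedy but do not remove the contradiction between the sections.

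The point cannot be left to a statistical analysis plan: who is tested at a visit and what defines a recruitment group belong in the protocol.

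**Conclusion.** The point holds in a limited form. The protocol gives three incompatible answers on which asthmatic children in WP III are skin-tested. The one in section 5.2 accepts results of any age and any panel for a grouping variable that has no stated definition. Outdated negatives may therefore dilute the allergic versus non-allergic contrast.

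The size is unknown. At an assumed 10% to 30% misclassification of the non-allergic group, the contrast keeps 90% to 70% of its true size, under one-way misclassification and unchanged variance. No planned power figure is shown to fail, because there is none. The WP III question of healthy versus asthmatic children does not depend on the split and is not affected. In an exploratory study this should be corrected, but it does not undermine WP III as a whole.

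**What to change.** Reconcile the Schedule, section 5.2 (WP III) and section 6.6:

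- Drop the never-tested condition for WP III. Do the seven-aeroallergen SPT at the visit, as the Schedule already marks, at least for every asthmatic child without a documented positive test.
- State the group definition in section 5.1 or 6.1, with the positivity criterion. Allergic: a documented positive test or a positive study SPT. Non-allergic: no documented positive and a negative current SPT. A current negative then never overrides a documented positive, and every child in the non-allergic group has been tested by the same method at the same visit.
- Correct the cystic fibrosis sentence in section 6.6.

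Cost: for the planned asthmatic children, at most 30 + 30 = 60 tests of 15 to 20 minutes, or 15 to 20 hours in all, and fewer where a positive is already documented. Some children will change group on the day, so recruitment per group must be tracked by test result. For example, if 20% of candidates for the non-allergic group tested positive, about 30 / 0.8 = 37.5, that is 38 candidates, would be needed to fill it.
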